7.3. Unscheduled Visits

If, during the investigation, a subject requires an unscheduled visit to the clinical site, the following information will be collected at a minimum:

- Chief complaint prompting the visit. If the reason is an adverse event, the applicable eCRF for the adverse event must be completed and subject record completed as appropriate
- Date and time of the visit and all procedures completed at the unscheduled visit
- Review of adverse event and concomitant medications
- Documentation of any test article dispensed or collected from the subject, if applicable

- Slit lamp findings (using the Slit Lamp Classification Scale)

If the Investigator withdraws a subject from the study, the final study visit case report forms must be completed indicating the reason(s) why the subject was withdrawn. The subject record must be completed documenting the date and primary reason for withdrawal and the study CRA notified.

Any ocular and non-ocular Adverse Events that are ongoing at the time of the study visit will be followed by the Investigator, within licensure, until they have resolved, returned to pre-treatment status, stabilized, or been satisfactorily explained. If further treatment ie, beyond licensure is required, the subject will be referred to the appropriate health care provider.

The following information may be collected during an unscheduled visit.

Unscheduled Visit			
Step	Procedure	Details	
U.1	Chief Complaints	Record the subject's chief complaints for reasons for the unscheduled visit.	
U.2	Adverse Events and Concomitant Medications Review	Review any changes to the subject's medical history or concomitant medications from the previous study visit. Record any changes, and any adverse events.	
U.3	Entrance VA	Record the logMAR distance visual acuity (OD and OS) with the subject's habitual spectacle correction, trial frame or unaided.	
U.4	Subjective Spherocylindrical Refraction	Perform bare-eye subjective spherocylindrical refraction with a phoropter (adopt the maximum plus to maximum VA (MPMVA) approach and use the duo-chrome test for binocular balancing) and record the best corrected distance VA to the nearest letter (OD, OS, and OU).	
U.5	Slit Lamp Biomicroscopy	FDA Slit Lamp Classification Scale will be used to grade the findings. If the clearance of the fluorescein needs to be expedited, preservative-free rewetting drops may be instilled.	
U.6	Dispensing (if applicable)	Additional lenses may be dispensed.	
U.7	Exit Visual Acuity	Record the subject's exit distance VA (OD, OS, and OU) to the nearest letter.	

7.4. Laboratory Procedures

Not applicable.

8. SUBJECTS COMPLETION/WITHDRAWAL

8.1. Completion Criteria

Subjects are considered to have completed the study if they:

- provided informed consent and/or assent;
- they are eligible;
- Completed all three phases of testing;
- Have not withdrawn/discontinued from the study for any reason described in Section 8.2.

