5.2. Masking

Due to visible difference between the lenses, it is difficult to completely mask subject, however subjects will be masked to the lens type and brand. Investigators will not be masked.

Under normal circumstances, the mask should not be broken until all subjects have completed the study and the database is finalized. Otherwise, the mask should be broken only if specific emergency treatment/course of action would be dictated by knowing the treatment status of the subject. In such cases, the Investigator may, in an emergency, contact the medical monitor. In the event the mask is broken the Sponsor must be informed as soon as possible. The date, time, and reason for the unmasking must be documented in the subject

record. The Investigator is also advised not to reveal the study treatment assignment to the clinical site or Sponsor personnel.

Subjects who have had their treatment assignment unmasked are expected to return for all remaining scheduled evaluations. Subjects who are discontinued may be replaced.

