		
 • The lenses will be worn as daily wear only. • Subjects will be given Revitalens solution, or Sponsor-approved alternative. • Rewetting drops are permitted if needed. • Subjects will be scheduled for their 11-14 day follow-up visit, ensuring that they wear the study lens at least 6 hours on the day of the follow-up visit. 
* Note: In the event a lens is lost or damaged, the subject will return to the clinical site for replacement. As much as reasonably possible, a damaged lens and packaging should be returned to the clinical site (wet, if possible) and then returned to the Sponsor. If lens damage is present, complete the PQC Form. The lens will be stored in labeled vial with saline, and clearly differentiated from the other worn lenses that will be shipped back to the Sponsor.
	
--	--	---	--

VISIT 4

The subjects must present to Visit 4 wearing test article for at least six (6) hours on the day of the visit. They will be asked to bring their spectacles to this visit (if applicable).

Visit 2: Treatment 1 Follow-Up			
Step	Procedure	Details	
4.1.	Adverse Events and Concomitant Medications Review	Review the subject's concomitant medications and record any changes from the previous study visit. Record any adverse events or medical history changes from the previous study visit.	
4.2.	Wearing Time	Record the average wearing time and comfortable wearing time.	
4.3.	Compliance	Confirm compliance with the prescribed wear schedule.	
4.4.	Subject Reported Ocular Symptoms	Subjects will respond to a verbal open-ended symptoms questionnaire.	
4.5.	Follow-Up Questionnaire	The subject will respond to the CLUE Follow-Up Questionnaire	Appendix A
4.6.	Distance ETDRS LogMAR Visual Acuity	Per [REDACTED] please confirm room illuminance and chart luminance are within acceptable ranges for both high/low contrast VA testing.	

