		
 1. Under high illumination and high chart luminance, record the distance (4 meter) ETDRS high contrast VA twice OD (HC1-HC2) and twice OS (HC3-HC4). 2. Under high illumination and high chart luminance, record the distance (4 meter) ETDRS low contrast VA twice OD (LC1-LC2) and twice OS (LC3-LC4). 3. With the goggles on, under normal illumination and chart luminance, record the distance (4 meter) ETDRS high contrast VA twice OD (HC5-HC26 and twice OS (HC7-HC8). Allow subject to adjust to dim condition for 3 minutes. 
Letter-by-letter results will be recorded into the electronic data capture form, which will calculate the visual performance score for each chart read.
	
4.7.	Cosmetic Lens Fit Assessment (without slit-lamp)	The Cosmetic Lens Assessment will be assessed by the investigator (without slit-lamp) in primary gaze and extreme gaze (right, left, and upgaze) at a normal conversation distance (approximately three (3) feet away from the subject).	Appendix D
4.8.	Hula Hoop Assessment (without slit-lamp)	The Hula Hoop Assessment will be assessed by the investigator (without slit-lamp) in primary gaze and extreme gaze (right, left, and upgaze) at a normal conversation distance (approximately three (3) feet away from the subject).	Appendix D
4.9.	Subjective Lens Fit Assessment	
Evaluate overall lens fit acceptance (acceptable or unacceptable) based on centration, movement and other fitting characteristics.
 
An unacceptable fit will be any one or more of the following criteria:
 
 • Presence of limbal exposure (appearance of clear cornea) in any gaze; • Presence of edge lift; • Presence of unacceptable movement (excessive or insufficient) in all three of the following conditions: primary gaze, up gaze, and Josephson push up. 
Note: if lens fit is unacceptable subject will be discontinued from the study.
	

4.10.	Wettability Characteristics	Record the white light lens wettability of both lenses.	████████
4.11.	Surface Deposits	Record any front and back surface lens deposits.	████████
4.12.	Remove lenses	The lenses will be removed and discarded.	

FINAL EVALUATION

The final evaluation will ordinarily take place immediately following the last scheduled follow-up visit per the study protocol. It may also take place at any point the subject discontinues the study or is terminated from the study.

Final Evaluation			
Step	Procedure	Details	████████

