F.1	Final Exam Form	Indicate if the subject completed the study successfully. If subject discontinued from the study, indicate the reason.	
F.2	Exit Slit Lamp Biomicroscopy	FDA Slit Lamp Classification Scale will be used to grade the findings and determine eligibility. If the clearance of the fluorescein needs to be expedited, preservative-free rewetting drops or saline may be instilled.	████████
F.3	Exit Visual Acuity	Record the distance logMAR VA (OD, OS) to the nearest letter with their habitual spectacle correction, or trial frame, in place under high illumination and high chart luminance. Record the distance (4 meter) ETDRS high contrast VA twice OD (HC1-HC2) and twice OS (HC3-HC4). Subjects must attempt each line after identifying the starting line until 3 or more letters are missed.	████████

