8.2. Withdrawal/Discontinuation from the Study

A subject will be withdrawn from the study for any of the following reasons:

- Subject death during the study period
- Subject withdrawal of consent
- Subject not compliant to protocol
- Subject lost to follow-up
- Subject no longer meets eligibility criteria (eg the subject becomes pregnant)
- Subject develops significant or serious adverse events causing discontinuation of study lens wear
- Subjects who have experienced a Corneal Infiltrative Event (CIE)
- Investigator's clinical judgment regarding the subject safety reasons (that it is in the best interest of the subject to stop treatment)

For discontinued subjects, the Investigator will:

- Complete the current visit (scheduled or unscheduled)
- Complete the Final Evaluation, indicating the reason that the subject was discontinued from the study
- Record the spherocylindrical refraction with best corrected distance VA
- Collect used test article(s) (worn or brought to the visit) from the subject and discard them, unless otherwise stated in Section 7.2
- Collect all unused test article(s) from the subject

An additional subject may be enrolled if a subject discontinues from the study prematurely.

In cases where a subject is lost to follow-up, every possible effort must be made to contact the subject and determine the reason for discontinuation/withdrawal. The measures taken to follow up must be documented including two written attempts and a certified letter (or equivalent) as the final attempt.

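### Does the loose definition of a completer (three undefined phases, and a fit failure at the last visit) put any result at risk?

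*Combined protocol and SAP*

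**What the plan says.** Section 8.1 sets four conditions for completion: consent, eligibility, "Completed all three phases of testing", and "Have not withdrawn/discontinued from the study for any reason described in Section 8.2". Section 8.2 opens its list with "A subject will be withdrawn from the study for any of the following reasons" and gives eight reasons: death, withdrawn consent, non-compliance, loss to follow-up, lost eligibility, significant or serious adverse events, a corneal infiltrative event, and the investigator's judgement on safety.

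Section 7.2, step 4.9 (Visit 4), has its own rule: "Note: if lens fit is unacceptable subject will be discontinued from the study". The same note stands at steps 1.26, 2.9 and 3.15. The Visit 4 table carries the heading "Visit 2: Treatment 1 Follow-Up". Form F.1 at the Final Evaluation then asks the site: "Indicate if the subject completed the study successfully. If subject discontinued from the study, indicate the reason".

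Two sections deal with replacement. Section 8.2 says "An additional subject may be enrolled if a subject discontinues from the study prematurely"; Section 5.2 says "Subjects who are discontinued may be replaced".

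The synopsis aims for about 40 completers from at most 50 enrolled, and Section 14.2 speaks of 20. The Per-Protocol set in Section 14.3 has its own wording on completing visits and does not cite 8.1.

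**The concern.** The number three matches neither the two lens periods nor the four visits, so one condition for completion cannot be applied literally.

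The second mismatch looks more serious. A subject with unacceptable fit at Visit 4 has attended every visit. Step 4.9 calls her discontinued. The last condition of 8.1 is not breached, because 8.2 does not list lens fit. F.1 wants one answer. Two sites could classify the same case differently, and both sample-size statements are expressed in completers. Replacement of the subject and her Per-Protocol membership could then also depend on the reading.

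**Working it through.** **1. Does the reading of three change who completes?** Section 4.1 mentions three follow-up visits after the first. The synopsis gives wear, washout, wear. Neither is called a phase, but both yield three. Counting what has been finished by the last visit attended:

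| Last visit finished | Follow-up visits done | Wear/washout/wear stages done |
|---|---|---|
| Visit 1 | 0 of 3 | 0 of 3 |
| Visit 2 | 1 of 3 | 1 of 3 |
| Visit 3 | 2 of 3 | 2 of 3 |
| Visit 4 | 3 of 3 | 3 of 3 |

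The columns agree in every row. A third, less natural reading is the three logMAR chart conditions. These are scheduled at all four visits, so finishing all of that testing also means reaching Visit 4.

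**2. Can a fit failure at Visit 4 be placed under a reason in 8.2?** Two routes come near.
- *Lost eligibility.* Lens fit is not an inclusion or exclusion criterion (3.2, 3.3). Section 6.3 counts dispensing requirements as eligibility requirements, and acceptable fit is a condition for continuing at steps 1.30 and 3.19. At Visit 4, however, nothing is dispensed, and step 4.12 takes the lenses off every subject.
- *Safety judgement.* Step 4.9 does not depend on safety.

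So 8.2 is silent on this case. It does not say that its list is exhaustive.

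**3. What would a site record?** Step 4.9 is explicit and F.1 follows it. A site that works through 7.2 in order enters a discontinuation with lens fit as the reason. The entry can be identified in the data whatever label is later used.

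**4. Which data depend on the label?**
- Primary endpoint: high-contrast logMAR at lens fitting (2.2), taken at Visits 1 and 3, before the question arises.
- Visit 4 data: the questionnaire (4.5) and logMAR (4.6) precede step 4.9, the fit result is recorded at 4.9, and 8.2 tells the investigator to finish the current visit and the Final Evaluation.
- Analysis: results are used when available (14.1), summarised by lens (14.5, 14.7), with no imputation (14.9). There is no test, and no summary is tied to the Per-Protocol set.

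**5. How large could the count be?** The documents give no fit-failure rate, so the rates are assumed: *a* and *b* per visit for the two lenses, independent across visits. With *n* subjects at Visit 4, half in each order, the expected number with unclear status is (n/2)(a + b). The total fit loss over four visits is 1 − (1 − a)²(1 − b)². It should stay within the all-cause loss implied by the synopsis, 1 − 40/50 = 20%.

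| a / b | Total fit loss | Unclear, n = 40 | Completers if excluded | Unclear, n = 20 |
|---|---|---|---|---|
| 1% / 2% | 5.9% | 20 × 0.03 = 0.6 | 39.4 | 0.3 |
| 2% / 5% | 13.3% | 20 × 0.07 = 1.4 | 38.6 | 0.7 |
| 5% / 5% | 18.5% | 20 × 0.10 = 2.0 | 38.0 | 1.0 |

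At 10% for both lenses the fit loss alone would be 1 − 0.9⁴ = 34.4%, beyond what the synopsis allows for. Independence probably overstates the counts: everyone at Visit 4 had an acceptable fit with the same lens at Visit 3, so if fit persists within a subject, later failures are rarer than the per-visit rate suggests.

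**The case for a change.** The best case for a change is that the mismatch is real and cheap to remove. The Per-Protocol question can wait for the cohort review committee before hard lock, but F.1 entries and replacement are decided during conduct. Status also changes what is collected: 8.2 asks for a refraction with best corrected acuity in discontinued subjects, and steps F.1 to F.3 do not ask for it in completers. Lens fit is itself a listed observation, so disposition would depend on an outcome seen at the last visit.

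Part of this stands. The term in 8.1 is undefined, 8.2 does not name lens fit, and the Visit 4 heading is wrong. The consequences are slight:
- Sites diverge only if one of them sets aside an explicit step by inference from 8.1.
- The two replacement sentences are both permissive. Neither forbids what the other allows, and the enrollment limit in the synopsis still applies.
- The extra refraction feeds no endpoint listed in 2.2.
- Visit dates and the Visit 4 fit result are recorded anyway (15.2, step 4.9), so attendance at all visits and fit at the last one can be tabulated separately without a new field.

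**Conclusion.** The phase wording and the Visit 4 heading are clerical slips. The status of a Visit 4 fit failure is a small gap that a disposition table by recorded reason fills. No endpoint, summary or conclusion changes. What can change is the completer count, by an expected 0.6 to 2.0 subjects of 40 at Visit 4 under assumed rates of 1% and 2% up to 5% and 5%, independent across visits. A count of 38.0 to 39.4 remains close to the synopsis target of about 40, which no hypothesis test depends on. This conclusion rests on the analysis staying descriptive, by lens and on available data. If a Per-Protocol fit table were added, the committee would have to settle these subjects' membership first, as 14.3 already provides. Step 4.9, F.1, 8.1 and 8.2 do not agree on this case and can be reconciled if the protocol is reopened for another reason. I take no view on which discontinuation rule should stand.

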8.2. Withdrawal/Discontinuation from the Study

A subject will be withdrawn from the study for any of the following reasons:

- Subject death during the study period
- Subject withdrawal of consent
- Subject not compliant to protocol
- Subject lost to follow-up
- Subject no longer meets eligibility criteria (eg the subject becomes pregnant)
- Subject develops significant or serious adverse events causing discontinuation of study lens wear
- Subjects who have experienced a Corneal Infiltrative Event (CIE)
- Investigator's clinical judgment regarding the subject safety reasons (that it is in the best interest of the subject to stop treatment)

For discontinued subjects, the Investigator will:

- Complete the current visit (scheduled or unscheduled)
- Complete the Final Evaluation, indicating the reason that the subject was discontinued from the study
- Record the spherocylindrical refraction with best corrected distance VA
- Collect used test article(s) (worn or brought to the visit) from the subject and discard them, unless otherwise stated in Section 7.2
- Collect all unused test article(s) from the subject

An additional subject may be enrolled if a subject discontinues from the study prematurely.

In cases where a subject is lost to follow-up, every possible effort must be made to contact the subject and determine the reason for discontinuation/withdrawal. The measures taken to follow up must be documented including two written attempts and a certified letter (or equivalent) as the final attempt.

9. PRE-STUDY AND CONCOMITANT INTERVENTION/MEDICATION

Concomitant medications will be documented during screening and updated during the study.

Disallowed medications for this study include: Not applicable.

Concomitant therapies that are disallowed include: Not applicable.

10. DEVIATIONS FROM THE PROTOCOL

Investigator will notify study sponsor upon identification of a protocol deviation. Major protocol deviations must be reported to the sponsor within 24 hours after discovery of the protocol deviation. The Investigator will report deviations per IRB/IEC requirements. All deviations will be tracked and corrective actions implemented as appropriate.

If it becomes necessary for the Investigator to implement a deviation in order to eliminate an immediate hazard to the trial subject, the Investigator may implement the deviation immediately without notification to the sponsor. Within 24 hours after the implemented deviation, the Investigator must notify and provide the rationale to the Sponsor and, as required, the IEC/IRB.

11. STUDY TERMINATION

The occurrence of one or more Unanticipated Serious Adverse Device Effect (USADE), or any SAE where the relationship to study agent cannot be ruled out, may result in stopping further dispensing of test article. In the event of a USADE or SAE, the Sponsor may unmask the treatment regimen for the subject(s) and will discuss this with the Investigator before any further subjects are enrolled.

The Sponsor will determine when a study will be stopped. The Principal Investigator always has the discretion to initiate stopping the study based on patient safety or if information indicates the study's results are compromised.

JJVC reserves the right to terminate the study at any time for any reason. Additionally, the IEC/IRB reserves the right to terminate the study if an unreasonable risk is determined. The study can be terminated by the Principal Investigator at the individual clinical site due to specific clinical observations, if in their opinion, after a discussion with JJVC, it is determined that it would be unwise to continue at the clinical site.

JJVC (and the IEC/IRB and DMC, if applicable) will evaluate all adverse events. If it is determined that an adverse event presents an unreasonable risk, the investigation, or that part of the investigation presenting the risk, will be terminated, as soon as possible.

Should the study be terminated (either prematurely or as scheduled), the Investigator will notify the IEC/IRB and Regulatory Authority as required by local regulatory requirements.

12. PROCEDURE FOR HANDLING PRODUCT QUALITY COMPLAINTS

A Product Quality Complaint refers to any written, electronic, or oral communication that alleges deficiencies related to the identity, quality, durability, reliability, safety, effectiveness or performance of test articles after they have been released for clinical trial use.

Potential complaints may come from a variety of sources including but not limited to subjects, clinical research associates (CRA), clinical operations managers (COM), medical monitors, and site personnel, etc. The following are not considered PQC's:

- Subject satisfaction inquiries reported via “Subjective Questionnaires” and “Patient Reported Outcomes (PRO)”
- Clinical test articles that are stored improperly or damaged after receipt at the investigational site
- Lens replacements that occur due to drops/fall-outs
- Damage deemed by clinicians or clinical staff to be caused by handling by the user, and not indicative of a quality deficiency (ie, tears, rips, etc.), only in situations where there is no deficiency alleged by the subject

Within 24 hours of site personnel becoming aware that a PQC has occurred, the PQC must be recorded in the EDC system, which will trigger an automatic email notification to the appropriate COM/CRA and Clinical QA representative. In cases where the EDC system in use is not configured to send automatic notifications or when an EDC system is not used, the COM/CRA is responsible for notifying Clinical QA upon discovery that a PQC has occurred.

Upon receipt of the EDC notification, the COM/CRA will contact the study site to collect additional information which will include:

- Date the complaint was received/recorded in the EDC System (Date of Sponsor Awareness)
- Who received the complaint
- Study number
- Clinical site information (contact name, site ID, telephone number)
- Lot number(s)
- Unique Subject Identifier(s)
- Indication of who first observed complaint (site personnel or subject)
- OD/OS indication, along with whether the lens was inserted
- Any related AE number if applicable
- Detailed complaint description (scheduled/unscheduled visit, wear time, symptoms, resolution of symptoms, etc.)
- Eye Care Provider objective (slit lamp) findings if applicable
- Confirmation of product availability for return (and tracking information, if available), or rationale if product is not available for return [REDACTED]

Once a complaint is received, it will be assessed by the COM, CRA, or trained site personnel to determine if it is an Adverse Event/Serious Adverse Event (AE/SAE). If the complaint results in an AE/SAE, the COM/CRA, or trained site personnel will follow Section 13 of this protocol. If the AE/SAE was potentially the result of a product quality related deficiency, these procedures also applies and will be executed in parallel.

In some cases, a PQC form may be generated in EDC by the site in error. In this event, the PQC forms will be marked “Intentionally Left Blank” or “ILB”. Justification for ILB must be documented.

